8.1.1 DEFINITION OF ADVERSE EVENTS (AE)

An adverse event will be defined as any untoward medical occurrence associated with the use of intranasal Verapamil HCl, whether or not it is considered related to the intervention.

8.1.2 DEFINITION OF SERIOUS ADVERSE EVENTS (SAE)

An AE or suspected adverse reaction is considered "serious" if, in the view of either the investigator or sponsor, it results in any of the following outcomes: death, a life-threatening adverse event, inpatient hospitalization or prolongation of existing hospitalization, a persistent or significant incapacity or substantial disruption of the ability to conduct normal life functions, or a congenital anomaly/birth defect. Important medical events that may not result in death, be life-threatening, or require hospitalization may be considered serious when, based upon appropriate medical judgment, they may jeopardize the patient or subject and may require medical or surgical intervention to prevent one of the outcomes listed in this definition.

8.1.3 DEFINITION OF UNANTICIPATED PROBLEMS (UP)

OHRP considers unanticipated problems involving risks to participants or others to include, in general, any incident, experience, or outcome that meets **all** of the following criteria:

- Unexpected in terms of nature, severity, or frequency given (a) the research procedures that are described in the protocol-related documents, such as the IRB-approved research protocol and informed consent document; and (b) the characteristics of the participant population being studied;
- Related or possibly related to participation in the research ("possibly related" means there is a reasonable possibility that the incident, experience, or outcome may have been caused by the procedures involved in the research); and
- Suggests that the research places participants or others at a greater risk of harm (including physical, psychological, economic, or social harm) than was previously known or recognized.

This study will use the OHRP definition of UP

8.2 CLASSIFICATION OF AN ADVERSE EVENT

8.2.1 SEVERITY OF EVENT

For AEs not included in the protocol defined grading system, the following guidelines will be used to describe severity.

- Mild Events require minimal or no treatment and do not interfere with the participant's daily activities.
- **Moderate** Events result in a low level of inconvenience or concern with the therapeutic measures. Moderate events may cause some interference with functioning.
- **Severe** Events interrupt a participant's usual daily activity and may require systemic drug therapy or other treatment. Severe events are usually potentially life-threatening or incapacitating.

8.2.2 RELATIONSHIP TO STUDY AGENT

The clinician's assessment of an AE's relationship to study agent (drug, biologic, device) is part of the documentation process, but it is not a factor in determining what is or is not reported in the study. If there is any doubt as to whether a clinical observation is an AE, the event should be reported. All AEs must have their relationship to study agent assessed. In a clinical trial, the study product must always be suspect. To help assess, the following guidelines are used.

- Related The AE is known to occur with the study agent, there is a reasonable possibility that the study agent caused the AE, or there is a temporal relationship between the study agent and event. Reasonable possibility means that there is evidence to suggest a causal relationship between the study agent and the AE
- Not Related There is not a reasonable possibility that the administration of the study agent caused the
 event, there is no temporal relationship between the study agent and event onset, or an alternate
 etiology has been established

8.2.3 EXPECTEDNESS

[name] will be responsible for determining whether an AE is expected or unexpected. An AE will be considered unexpected if the nature, severity, or frequency of the event is not consistent with the risk information previously described for the study agent.

8.3 TIME PERIOD AND FREQUENCY FOR EVENT ASSESSMENT AND FOLLOW-UP

Participants will be assessed for AEs during each study visit. All AEs including local and systemic reactions not meeting the criteria for SAEs will be recorded in the CRF. Information to be collected includes event description, time of onset, clinician's assessment of severity, relationship to study product (assessed only by those with the training and authority to make a diagnosis), and time of resolution/stabilization of the event. All AEs will be followed to adequate resolution.

Any medical condition that is present at the time that the participant is screened will be considered as baseline and not reported as an AE. However, if the study participant's condition deteriorates at any time during the study, it will be recorded as an AE. UPs will be recorded in the participant file throughout the study.

Changes in the severity of an AE will be documented to allow an assessment of the duration of the event at each level of severity to be performed. AEs characterized as intermittent require documentation of onset and duration of each episode.

The PI will record all reportable events with start dates occurring any time after informed consent is obtained until 7 (for non-serious AEs) or 30 days (for SAEs) after the last day of study participation. At each study visit, the investigator will inquire about the occurrence of AE/SAEs since the last visit. Events will be followed for outcome information until resolution or stabilization

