6.1.9 DURATION OF THERAPY

Phase Ib participants will undergo therapy for at least 1 week. Total therapy time will be determined by the number of dose escalations a participant is given.

Phase II participants will undergo therapy for 4 weeks.

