7.3.4 FINAL STUDY VISIT

Phase 1B:

Participants will have their final study visit when they experience DLT and are removed from the study, choose to end their participation, or achive the maximal administered dose. The reason for the drop-out will be noted in the participant file. Participants will be asked to fil out a SNOT-22, VAS, Satisfaction scale, and Compliance scale and will be evaluated for side-effects. An endoscopy will be recorded and scored. A mucus sample will be collected from the nasal cavity with a small sponge. Participants will receive their compensation at the end of the final visit.

Phase 2:

During the Week 4 visit participants will be asked to fill out a SNOT-22, VAS, Satisfaction scale, and Compliance scale. Adherence to the treatment regimen will be evaluated. Participants will be evaluated for side-effects. An endoscopy will be recorded and scored. A mucus sample will be collected from the nasal cavity with a small sponge. Participants will receive their compensation at the end of the final visit.

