7.3.5 EARLY TERMINATION VISIT

In the event of an early termination participants will be asked to perform all the procedures for the final visit (Phase 1B and 2) at their final visit.

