7.3.7 SCHEDULE OF EVENTS TABLE

4	Phase Ib			Phase II			
Procedures	Screening	Enrollment/ Baseline	Weekly/Final Follow-up	Screening	Enrollment/ Baseline	Follow-up (Day 7)	Final Visit (Day 28)
Informed Consent (IC)	X		-	х			
Intake Form (IF)	X	3	į	x		3	
Pregnancy Test (PT)	X			x			
SNOT-22	100	х	х		х	х	X
Visual Analog Scale (VAS)	3	х	x		х	х	X
Electrocardiogram (EKG)		х	х		x	x	
Heart Rate (HR)		х	х		х	х	X
Blood Pressure (BP)	ŝ.	x	x		x	x	х
Lund-Kennedy Score (LKS)		x	x		х	x	X
Nasal irrigation (NI)		х	х		х		х
Mucus sponge (MS)	ý.	x	х		x	- 3	х
Satisfaction Scale (SS)		d	x			Х	х
Compliance Scale (CS)			×			×	х
Side effects (SE)			x			х	X

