10.4.7 PLANNED INTERIM ANALYSES

10.4.7.1 SAFETY REVIEW

Phase Ib:

This arm will be halted when the MTD has been determined. The proposed safety endpoints will be monitored at each weekly visit. Participants will be formally queried for medication related side effects and will undergo an EKG at each visit, which will be assessed by a medical internist/anesthesiologist.

Phase II:

This arm will be halted if 20% of the population experiences a severe adverse event. This decision will be made at the discretion of the DSMB. Safety endpoints will be monitored at each of the 3 study visits (baseline, week 1, week 4). Participants will be formally queried for medication related side effects and will undergo a repeat EKG at the week 1 visit, which will be assessed by a medical internist/anesthesiologist.

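### The AE and SAE recording windows run 7 and 30 days past the last participation day, but no study contact is scheduled to ask completers about that time

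*Combined protocol and SAP*

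**What the plan says.** Section 8.3 opens the recording window at informed consent and keeps it open "until 7 (for non-serious AEs) or 30 days (for SAEs) after the last day of study participation". For finding events, the same section says "Participants will be assessed for AEs during each study visit" and "At each study visit, the investigator will inquire about the occurrence of AE/SAEs since the last visit". It describes no other form of inquiry.

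In Phase II, "Phase II participants will undergo therapy for 4 weeks" (6.1.9). The last Phase II column of the schedule of events (7.3.7) is headed "Final Visit (Day 28"), and 10.4.7.1 says "Safety endpoints will be monitored at each of the 3 study visits (baseline, week 1, week 4"). In Phase Ib, 7.3.4 says "Participants will have their final study visit when they experience DLT and are removed from the study"; the other triggers it gives are the participant's own choice to stop and reaching the maximal administered dose. Section 7.3.5 adds "In the event of an early termination participants will be asked to perform all the procedures for the final visit". None of these sections lists a later visit, call or form.

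Later follow-up exists for three groups: participants who withdraw or are terminated because of an AE, for up to one year (5.4.2); participants with an event already identified, until it resolves or stabilises (8.3, 8.4.2); and participants who become pregnant (8.4.5).

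**The concern.** The window and the method for filling it sit in the same section and do not match. Asking at each visit about the time since the previous visit covers everything up to the final visit and nothing after it. A completer with no open event has no later visit at which the question could be put.

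Safety is part of the Phase II primary objective (section 3), and 10.4.4 judges it by the rate of adverse events. With 20 Phase II participants, a few missed cases would be visible in that rate. If post-treatment events are collected only when someone happens to report them, a count for the full window mixes actively collected data with passively collected data. A reader of the results could not tell where one stops and the other starts.

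**Working it through.** The plan states no figure to reproduce. The check sets the window against the contact schedule and counts days.

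**Inputs**
- Window after the last participation day: 7 days for non-serious AEs, 30 days for SAEs (8.3).
- Last scheduled Phase II contact: Day 28 (7.3.7). Treatment also lasts 4 weeks, so taking the last participation day as the final visit or as the last dose gives about the same date.
- Window start: consent (8.3). Screening may be followed by a 3-week steroid washout before the trial begins (7.3.1).
- Phase II sample size: 20 (4.1). Total population: 20 to 40 (Protocol Summary).

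**Phase II, counted from first dose as Day 0**
- The non-serious AE window ends at 28 + 7 = Day 35. Share with no scheduled inquiry: 7/35 = 20%.
- The SAE window ends at 28 + 30 = Day 58. Share with no scheduled inquiry: 30/58 = 52%.

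**Phase II, counted from consent, assuming consent at the start of a full 21-day washout**
- Non-serious AEs: 7/(21 + 28 + 7) = 7/56 = 12.5%.
- SAEs: 30/(21 + 28 + 30) = 30/79 = 38%.

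For a Phase II completer the first pair is therefore the upper bound. The 7 and 30 uncovered days are the same under either count.

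**Phase Ib.** The share depends on how many dose levels a participant goes through. With all six levels in 6.1.7 at the minimum of one week each (42 days), counted from first dose, the shares are 7/49 = 14% and 30/72 = 42%. Fewer levels give larger shares.

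**Who is left uncovered.** The three follow-up groups are all defined by something already found: an AE that led to exit, a known event, or a pregnancy. None of those provisions looks for a new event in anyone else. A participant who completes without an open event is outside all three. So is one who leaves early for a reason other than an AE, because 7.3.5 only repeats the final-visit procedures.

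**Scale of one case.** In Phase II, one participant is 1/20 = 5 percentage points. The 10% mark in 10.4.4 corresponds to 2 of 20, and a 20% mark to 4 of 20. This gives the weight of one missed participant; it does not show that the gap would miss one.

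**The case against.** A reader might infer that the post-visit window is not observed at all. The documents do not support that. Section 8.3 obliges the investigator to record events with start dates inside the window however they become known, and the reporting clocks in 8.4.1 and 8.4.2 run from awareness, which can be passive. Section 7.1.2 lists a clinic examination every 2 to 4 weeks as routine care for Phase II patients. Participants come from the single recruiting clinic, and section 11 counts medical records and office charts as source documents. If routine care continues, some completers may be seen inside the 30 days. Instructions to telephone the site may also stand in the consent form, which is not among the pages available here. All of this stands, and it limits the point to active ascertainment. None of it is a scheduled AE inquiry.

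A reader might also infer that the 10% and 20% rates omit a period the protocol says they cover. That is not supported either. Sections 8.5, 10.4.4 and 10.4.7.1 state no period for these rates. Nor are the 20% rules the same: 8.5 refers to any AE, while 10.4.7.1 refers to severe events in Phase II. What remains is that the period is unstated.

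Finally, days are not risk. Section 2.3.1 expects cardiac effects to be dose-dependent and mostly reversible once the drug is stopped, so days off drug should carry less drug-related risk than treated days. This is fair, and the day shares should not be read as shares of expected events. Against it, 8.1.1 counts events whether or not they are thought related, and the schedule marks nasal irrigation at the Day 28 visit, so exposure may run up to the last day on which anyone asks.

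**Conclusion.** The point holds in a limited form. For completers with no open event, the plan has no procedure that actively covers the last 7 days of the non-serious AE window or the last 30 days of the SAE window. In Phase II this is at most 20% and 52% of the respective windows counted from first dose, and less counted from consent. Events in that time depend on spontaneous report or on chance awareness at routine care.

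The conclusion assumes that the last participation day, which the protocol does not define, falls at about the final visit, and that the schedule of events is complete. No event rate is available, so the number of events likely to be missed cannot be estimated. The efficacy analysis, the determination of the maximal tolerated dose, and safety data up to the final visit are not affected. This is a low-cost improvement in safety ascertainment and clarity; it does not undermine the trial.

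**What to change.** Add to 7.3.7 and 8.3 a short scripted telephone contact at the end of the 7-day window and another at the end of the 30-day window, for every participant in both phases. A single call at 30 days or later that asks about both periods would also serve. Define the last day of study participation, and state the period over which AE and SAE rates are computed.

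If no call is added, say so in 8.3, report AE rates as covering events up to the final visit only, and list later events separately as spontaneously reported.

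The cost is one or two brief coordinator calls for each of 20 to 40 participants, or 20 × 1 = 20 to 40 × 2 = 80 calls, plus a schedule amendment. Nothing in dosing or clinical management changes.

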8.4 REPORTING PROCEDURES

8.4.1 ADVERSE EVENT REPORTING

All AE's will be reported to both the IRB and DSMB. SAEs will be reported within 24 hours of investigator awareness and non-serious AEs will be reported within 7 days of investigator awareness. The study coordinator will compile a formal report of the event and corrective steps for both the DSMB and IRB. The investigator will be responsible for signing off on AE reports and submitting them to the DSMB and IRB.

8.4.2 SERIOUS ADVERSE EVENT REPORTING

The study clinician will complete a SAE Form within the following timelines:

- All deaths and immediately life-threatening events, whether related or unrelated, will be recorded on the SAE Form and submitted to the DCC/study sponsor within 24 hours of site awareness. See Section 1, Key Roles for contact information.
- Other SAEs regardless of relationship, will be submitted to the DCC/study sponsor within 72 hours of site awareness.

All SAEs will be followed until satisfactory resolution or until the site investigator deems the event to be chronic or the adherence to be stable. Other supporting documentation of the event may be requested by the DCC/study sponsor and should be provided as soon as possible. The study sponsor will be responsible for notifying FDA of any unexpected fatal or life-threatening suspected adverse reaction as soon as possible but in no case later than 7 calendar days after the sponsor's initial receipt of the information.

8.4.3 UNANTICIPATED PROBLEM REPORTING

Incidents or events that meet the OHRP criteria for UPs require the creation and completion of an UP report form. It is the site investigator's responsibility to report UPs to their IRB. The UP report will include the following information:

- Protocol identifying information: protocol title and number, PI's name, and the IRB projectnumber;
- A detailed description of the event, incident, experience, or outcome;
- An explanation of the basis for determining that the event, incident, experience, or outcome represents an UP
- A description of any changes to the protocol or other corrective actions that have been taken or are proposed in response to the UP.

To satisfy the requirement for prompt reporting, UPs will be reported using the following timeline:

- UPs that are SAEs will be reported to the IRB within 24 hours of the investigator becoming aware of the
 event
- Any other UP will be reported to the IRB within 7 days of the investigator becoming aware of the problem.

8.4.4 EVENTS OF SPECIAL INTEREST

N/a

8.4.5 REPORTING OF PREGNANCY

Pregnant women will be excluded from this trial. If a participant becomes pregnant during the trial they will be withdrawn and treatment will be immediately halted. The participant will then have safety follow-ups during the course of their pregnancy.

8.5 STUDY HALTING RULES

Administration of study agent will be halted if the trial reaches a 20% AE rate and enrollment screens will stop accepting new study participants. The PI will inform the DSMB members within 24 hours of this occurrence and will provide the DSMB with AE listing reports. The DSMB will convene an ad hoc meeting by teleconference or in writing as soon as possible. The DSMB will provide recommendations for proceeding with the study to the PI. The PI will inform the FDA of the temporary halt and the disposition of the study.

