5.5 PREMATURE TERMINATION OR SUSPENSION OF STUDY

This study may be temporarily suspended or prematurely terminated if there is sufficient reasonable cause. Written notification, documenting the reason for study suspension or termination, will be provided by the suspending or terminating party to the investigator. If the study is prematurely terminated or suspended, the PI will promptly inform the IRB and will provide the reason(s) for the termination or suspension.

Circumstances that may warrant termination or suspension include, but are not limited to:

- Determination of unexpected, significant, or unacceptable risk to participants including a greater than 20% AE rate
- Demonstration of efficacy that would warrant stopping
- Insufficient compliance to protocol requirements
- Data that are not sufficiently complete and/or evaluable
- Determination of futility

Study may resume once concerns about safety, protocol compliance, data quality are addressed and satisfy the sponsor, IRB and/or FDA.

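### Sections 8.5, 10.4.7.1 and 5.5 give Phase II three different halting rules at or above 20%, and nothing says which one governs

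*Combined protocol and SAP*

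**What the plan says.** Three places in the combined protocol and SAP set a criterion at or above 20% that applies to Phase II.

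- **Section 8.5, Study Halting Rules.** The trigger is worded as follows: "Administration of study agent will be halted if the trial reaches a 20% AE rate". Recruitment stops at the same point: "enrollment screens will stop accepting new study participants". The PI informs the DSMB within 24 hours, and the DSMB meets ad hoc and makes recommendations. The halt is described as temporary: "The PI will inform the FDA of the temporary halt and the disposition of the study".
- **Section 10.4.7.1, Safety Review, Phase II.** "This arm will be halted if 20% of the population experiences a severe adverse event". The next sentence reads: "This decision will be made at the discretion of the DSMB".
- **Section 5.5, Premature Termination or Suspension of Study.** The list opens with "Circumstances that may warrant termination or suspension include, but are not limited to". Its first item is "Determination of unexpected, significant, or unacceptable risk to participants including a greater than 20% AE rate".

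For Phase Ib, section 10.4.7.1 has no event-rate rule. It says only "This arm will be halted when the MTD has been determined".

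Section 8.1.1 counts an adverse event whether or not it is related to the drug. Section 8.2.1 makes severe the top of three grades. Section 2.3.1 already names nasal irritation and constipation as risks.

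**The concern.** A halting rule should give one answer on one set of data. Here the answer depends on which section the reader opens. Section 8.5 obliges the PI to stop dosing and enrollment once events of any grade reach 20%. Someone working from section 10.4.7.1 would see no trigger until 20% had severe events, and would then wait for the DSMB to decide.

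Mild events are foreseeable with a nasal rinse, so the two rules are likely to part company in practice. What follows once the 8.5 mark is reached is clear. What the text leaves open is when that mark is reached, and whether 10.4.7.1 replaces it, adds to it or describes a later stop. The duties to notify the DSMB within 24 hours and to inform the FDA depend on the answer. The drug is cardioactive (section 2.3.1).

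**Working it through.** **The rules side by side (Phase II)**

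| | 8.5 | 10.4.7.1 | 5.5 |
|---|---|---|---|
| Event | any AE | severe AE | any AE |
| Comparison | reaches 20% | 20% | above 20% |
| Base | the trial, otherwise undefined | the arm's population, undefined | undefined |
| Unit | not stated | participants | not stated |
| Force | will be halted | will be halted, at DSMB discretion | may warrant |
| First actor | PI | DSMB | not stated |

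**Turning 20% into counts.** Section 4.1 plans 20 Phase II participants. The plan's figure reproduces: with a difference of 15.9, SD 24 and two-sided alpha 0.05 (sidedness assumed), the exact one-sample t-test has power 0.802 at n = 20 and 0.780 at n = 19. Since 0.20 × 20 = 4, reaching 20% takes 4 participants and exceeding it takes 5.

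**Two test cases, counted over Phase II alone**

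1. Four of 20 have mild events. Section 8.5: halt. Section 10.4.7.1: not met. Section 5.5: 20.0% is not above 20%.
2. Four of 20 have severe events. Section 8.5: automatic halt. Section 10.4.7.1: mark met, but the DSMB decides. Section 5.5: still not exceeded.

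**How far apart the two main rules are.** The documents give no event rates, so every rate here is an assumption. For one check at 20 participants:

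P(X ≥ 4) = 1 − Σ(k=0 to 3) C(20,k) p^k (1−p)^(20−k)

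With 40% having any event, 8.5 is met with probability 0.984. With 5% having a severe event, 10.4.7.1 is met with probability 0.016.

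**What the undefined base and comparison add.** Let f_n(x) be the probability that x of the first n participants are affected and no check has yet met the mark. Then f_n(x) = f_(n−1)(x)(1−p) + f_(n−1)(x−1)p. At each check, the probability on counts that meet the mark is removed and added to the total. Participants are taken as independent, in enrollment order, with event status known at each check.

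Chance of meeting an any-event mark within 20 participants (reaches 20% / exceeds 20%):

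| Checks | p = 10% | 20% | 30% | 40% |
|---|---|---|---|---|
| At 20 only | 0.133 / 0.043 | 0.589 / 0.370 | 0.893 / 0.763 | 0.984 / 0.949 |
| At 10 and 20 | 0.296 / 0.089 | 0.724 / 0.456 | 0.935 / 0.808 | 0.991 / 0.961 |
| Each participant from 10 | 0.314 / 0.182 | 0.744 / 0.627 | 0.942 / 0.900 | 0.992 / 0.984 |
| Each participant from 1 | 0.486 / 0.429 | 0.825 / 0.782 | 0.962 / 0.946 | 0.995 / 0.992 |

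Ten participants is the Phase II DSMB review point in section 9. The documents fix none of these schedules for the halting rules.

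The same recursion for 10.4.7.1 (20% with severe events) at assumed severe rates of 2% and 5% gives 0.0006 and 0.016 on all 20, 0.017 and 0.096 on a running base from participant 10, and 0.100 and 0.249 on a running base from the first participant.

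**Pooling the phases.** If the trial in 8.5 means both phases, the completed total is at least 21 unless Phase Ib patients re-enroll. Then 4/21 = 19.0%, below the mark, and 5 are needed. At 40, the top of the range in the Protocol Summary, 8 are needed. Replacement of withdrawn participants (section 5.4.1) enlarges the enrolled base further.

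**The case against.** The strongest reply is that the rules can coexist. Section 10.4.7.1 does not say the arm halts only at 20% severe events, so a site facing four mild events can pause under 8.5 without breaching it. The 8.5 halt is temporary, 10.4.7.1 could be a later DSMB decision on the arm, and 5.5 is an open list. Read that way, the plan has a natural sequence.

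Part of this stands. Section 8.5 can be obeyed without breaching 5.5, and a tiered reading is possible. But the text never states the tiers, 10.4.7.1 does not refer to 8.5, and both say the agent or arm will be halted. The coexistence argument also covers only mild events: at 20% severe events, one section halts automatically and the other leaves the halt to the DSMB.

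It is also fair that four of 20 sits on the boundary and fails to trigger 8.5 on a pooled base. Larger counts of mild events still separate the rules. Checking after every participant is nowhere specified; with checks at 10 and 20 only, the range at a 10% rate narrows to 9% to 30%. Section 10.4.4 speaks of occurrence within the study population, which lends some support to counting participants rather than events, but it is not a halting rule.

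The DSMB charter (section 8.6) may define some terms. It is not among the documents, and the protocol sections would still differ.

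**Conclusion.** The concern holds. The main conflict is between 8.5 and 10.4.7.1, which differ in event class and in who decides. Section 5.5 adds a different comparison and a weaker force. This follows from the wording alone and needs no assumed rate.

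The size does rest on assumptions. At 40% any-event and 5% severe-event rates, one check at 20 gives 0.98 against 0.016. At a 10% any-event rate, the choice of comparison and base moves the chance of meeting the mark between 4% and 49%, the upper end being a running check from the first participant.

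Phase Ib is secondary. Only 8.5 and 5.5 apply there, and they differ in comparison and force. If the 8.5 rate is read as participants affected among those treated so far, one event in the first five treated meets it (1/5 = 20%). No section says how that pause fits with recruiting two more patients after a dose-limiting toxicity (section 4.1). That is a missing cross-reference, not a contradiction.

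**What to change.** Reconcile sections 5.5, 8.5 and 10.4.7.1 into one halting rule, or explicit tiers, for each phase. For each rule, state:

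- the event class;
- whether the mark is reached or must be exceeded;
- whether events or affected participants are counted;
- the denominator (treated to date, enrolled including replacements, or planned; one phase or both) and when it is evaluated;
- who decides;
- whether the result is a pause or a stop.

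Add a cross-reference to the escalation and expansion rules in section 4.1, and align the DSMB charter. Which rule and threshold govern is for the sponsor and the DSMB; none is proposed here.

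The cost is one wording amendment with IRB review and the charter alignment. No extra patients or visits are needed.
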